# 6.9 Contraception

All subjects must practice a highly effective method of contraception that may include, but is not limited to, abstinence, sex only with persons of the same sex, monogamous relationship with a postmenopausal partner, monogamous relationship with vasectomized partner, vasectomy, surgical sterilization (hysterectomy, bilateral tubal ligation, salpingectomy, or oophorectomy), licensed hormonal methods, IUD, or consistent use of a barrier method (eg, condom, diaphragm) with spermicide through Day 29.

# 6.10 Compliance

All IPs will be administered by trained personnel at the investigational site.

05 October 2017 Confidential Page 31 of 66

#### 7 STUDY ASSESSMENTS AND DATA COLLECTION

Refer to Section 1.2. for the Schedule of Events.

# 7.1 Demographics

Demographic data and other baseline characteristics will be obtained and recorded at Screening.

# 7.2 Medical History

A standard medical, medication, and surgical history will be obtained and recorded at Screening.

# 7.3 Reactogenicity (Diary)

Each subject will be provided with a diary and a thermometer after each dose. The subjects will record and provide severity grade (except for temperature) for the following items in a diary (sample provided in Appendix 2) and whether any medication or treatment was used for the symptom(s) daily for the first 14 days after dosing.

- Local events: nasal irritation, sneezing, nasal congestion, cough, sore throat, change in smell, change in taste, change in vision, eye pain
- Systemic events: headache, fatigue, muscle ache, nausea, vomiting, diarrhea, chills
- Oral temperature

If there are any events ongoing after the diary reporting period, these events will be followed until resolution and the stop date recorded. The Investigator (or Subinvestigator) will review the diary with the subject. Any changes or comments to the subject's diary by the Investigator (or Subinvestigator) must be made on the diary and initialed and dated by the Investigator (or Subinvestigator).

A reactogenicity event recorded on the diary will not be recorded as an AE unless it meets the criteria of an SAE.

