# 1 PROTOCOL SUMMARY

# 1.1 Synopsis

Sponsor: Altimmune, Inc.						
Study Title: Single-ascending-dose Study	Study Title: Single-ascending-dose Study of the Safety and Immunogenicity of NasoVAX					
Study Number: ALT-103-201	Study Phase: 2a					
Study Objectives and Endpoints:						
OBJECTIVES	ENDPOINTS					
Prir	nary Objective					
• To describe the safety profile of NasoVAX in healthy adults when administered by intranasal spray at a single dose of 1×10  , 1×10  , or 1×10  viral particles (vp)	• Reactogenicity: counts and percentages of subjects with local events (nasal irritation, sneezing, nasal congestion, cough, sore throat, change in smell, change in taste, change in vision, eye pain) and systemic events (headache, fatigue, muscle ache, nausea, vomiting, diarrhea, chills, fever) for 14 days after vaccination					
	Adverse events (AEs): counts and percentages of subjects with AEs from Day 1 to Day 29; medically attended AEs (MAEs), serious AEs (SAEs), new-onset chronic illnesses (NCIs) from Day 1 to Day 181					
Secon	ndary Objective					
• To evaluate the humoral immune response to NasoVAX when administered by intranasal spray at a single dose of 1×10  , 1×10  , or 1×10  vp	
 
Antibody level measured by hemagglutination inhibition (HAI) in serum:
 
Geometric mean titer (GMT): the antilog of the mean of the log-transformed titers
 
Geometric mean ratio (GMR): the ratio of postvaccination and prevaccination GMTs within the same dose group
 
Seroprotection rate (SPR): the percentage of subjects with a HAI titer ≥ 1:40
 
Seroconversion rate (SCR): the percentage of subjects with either a baseline HAI titer
 
< 1:10 and a postvaccination titer ≥ 1:40 (which is 4 times the assay lower limit of quantitation), or a baseline HAI titer ≥ 1:10 and a 4-fold increase in postvaccination HAI titer relative to baseline
 
					
	
 
Antibody level measured by microneutralization in serum:
 
GMT
 
Responder rate: the proportion of subjects with 2-fold and 4-fold rise since baseline
 
					

Altimmune, Inc.
Protocol

ALT-103-201
Version 4.0

	Exploratory Objectives						

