# 2.5 Previous Clinical Experience with Adenoviral Vectors

The ability of RD-Ad5 vectors to adequately express the protein of interest following parenteral administration in the presence of pre-existing immunity to wild-type (WT) Ad5 has been a concern [Yang1994]. However, several lines of evidence, including clinical trials of earlier formulations of NasoVAX, suggest that anti-Ad5 immunologic components may not represent the same barrier to efficacy when the vector is administered using the intranasal route and that administration by this route may overcome pre-existing immunity to the adenovirus vector.

A significant body of evidence supports the general safety of RD-Ad5 vectors, including lack of potential for replication and recombination with WT adenovirus. The Sponsor's previous nonclinical and clinical experience with Ad5-vectored vaccines has shown no evidence suggestive of viral recombination in vaccinated subjects.

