In a 2007 study of an Ad5-vectored vaccine encoding the HA surface protein antigen from the A/Vietnam/1203/2004(H5N1) influenza virus strain, 48 subjects were randomized for intranasal administration in groups of 12 to receive  $5.0 \times 10^7$  vp,  $2.4 \times 10^8$  vp,  $3.3 \times 10^9$  vp, or placebo 28 days apart. A total of 36 women and 12 men aged 25 to 40 (mean 34.0) years were enrolled. No SAEs and no anaphylaxis, hives, or other allergic reactions were reported. The most common local reactogenicity events were headache, runny nose, sore throat, nasal congestion, and nasal irritation and were predominantly mild. Incidence rates of reactogenicity events, unsolicited AEs, and abnormal physical examination findings, and shift rates from normal to abnormal laboratory results were not statistically significantly different between active and placebo groups. Although only 1 subject (8.3%) in the highest dose group seroconverted, 4 of the 12 (33%) had increases in HAI titer. Pre-existing immunity to the adenovirus vector was not associated with influenza antibody response.

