#### 4.2.3 Assessments

# Safety

An evaluation of safety is the primary objective for this study of NasoVAX that will evaluate doses higher than tested in the previous Phase 1 studies of this adenoviral vector. Safety assessments are standard for early-phase clinical trials and are in accordance with the US Food and Drug Administration's (FDA's) guidance on preventive vaccine clinical trials [FDA 2007b]. Reactogenicity events were requested by the FDA for intranasal administration.

Although NasoVAX is constructed from an RD adenoviral vector, there is a theoretical risk of recombination with WT adenovirus. Clinical illness caused by adenovirus can present as a wide variety of syndromes, including upper respiratory infection, pneumonia, conjunctivitis, and gastroenteritis [Adenoviruses 2015]. Subjects presenting with a potentially compatible clinical syndrome after vaccination will have appropriate specimens obtained for viral culture.

On the basis of animal biodistribution studies, it is expected that carriage of the vaccine vector will be transient and limited to the upper respiratory tract. Swab samples will be obtained for adenovirus qPCR to determine how long the vector persists at the site of administration.

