#### 5.2 Exclusion Criteria

Subjects who meet any of the following criteria will be excluded from the study:

- 1. Pregnant, possibly pregnant, or lactating women
- 2. Household contacts of pregnant women, children <5 years of age, or immunocompromised individuals for the period up through 2 weeks postvaccination
- 3. Persons who care for pregnant women, children <5 years of age, or immunocompromised individuals for the period up through 2 weeks postvaccination
- 4. Body mass index  $> 35.0 \text{ kg/m}^2$
- 5. Positive results for HIV, hepatitis B virus, or hepatitis C virus at Screening
- 6. Asthma or other chronic lung disease that is greater than mild in severity. Specifically excluded are participants with the any of the following events in the past year:
  - Daily symptoms
  - Daily use of short acting beta 2 agonists
  - Use of inhaled steroids or theophylline
  - Use of pulse systemic steroids
  - Emergency care or hospitalization related to asthma or other chronic lung disease
  - Systemic steroids for asthma exacerbation
- 7. History of diabetes mellitus (gestational diabetes is allowed if treatment was not required postpartum and serum glucose is currently in the normal range)
- 8. History of coronary artery disease, arrhythmia, or congestive heart failure
- 9. Clinically significant ECG abnormality as determined by the Investigator
- 10. Poorly controlled hypertension (systolic blood pressure >150 mmHg or diastolic blood pressure >95 mmHg) at Screening or predose on Day 1
- 11. History of anaphylaxis or angioedema
- 12. Known allergy to any of the ingredients in the vaccine formulation
- 13. History of chronic rhinitis, nasal septal defect, cleft palate, nasal polyps, or other nasal abnormality that might affect vaccine administration
- 14. Previous nasal surgery or nasal cauterization
- 15. Any symptoms of upper respiratory infection or temperature >38°C within 3 days before Day 1
- 16. Any symptoms within 24 hours before Day 1 of upper respiratory illness of allergy flareup that, in the opinion of the Investigator, presents as nasal congestion or rhinorrhea that could inhibit the proper administration of the IP

05 October 2017 Confidential Page 26 of 66

17. Known or suspected malignancy, excluding non-melanoma skin cancers and other early stage surgically excised malignancies that the Investigator considers to be exceedingly unlikely to recur

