#### 9.2 Reporting Responsibilities and Periods

It is the responsibility of the Investigator or Subinvestigator(s) to perform periodic assessment of AEs. AEs spontaneously reported by the subject or reported in response to an open question from the study personnel (eg, 'Have you had any health problems since the previous visit/you were last asked?') or revealed by observation will be recorded.

All AEs (including MAEs, NCIs, and SAEs) with onset after signing of the ICF until Day 29 will be recorded. Thereafter to the end of study, only MAEs, NCIs, and SAEs will be recorded. Data describing AEs will be recorded in the subject's medical and as appropriate, an SAE report form. SAEs will be reported to the Sponsor as described in Section 9.7.

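### Runny nose, among the most common local reactions in the earlier intranasal Ad5-influenza trial, is not solicited in the diary, so the reactogenicity endpoint has no prompted, graded record of it

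*Protocol*

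**What the plan says.** The reactogenicity endpoint rests on a closed list. The Synopsis (Section 1.1) gives "local events (nasal irritation, sneezing, nasal congestion, cough, sore throat, change in smell, change in taste, change in vision, eye pain", Section 3 repeats it, and Section 7.3 carries it into the diary as "Local events: nasal irritation, sneezing, nasal congestion, cough, sore throat, change in smell, change in taste, change in vision, eye pain". The other diary items are "Systemic events: headache, fatigue, muscle ache, nausea, vomiting, diarrhea, chills", plus oral temperature. The Appendix 2 diary and its severity guide have the same rows and no row for other symptoms.

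On earlier experience, Section 2.6 says of the 2007 intranasal trial: "The most common local reactogenicity events were headache, runny nose, sore throat, nasal congestion, and nasal irritation and were predominantly mild". Exclusion criterion 16 in Section 5.2 concerns symptoms that the investigator judges to be something that "presents as nasal congestion or rhinorrhea that could inhibit the proper administration of the IP".

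On the origin of the list, Section 4.2.3 says: "Reactogenicity events were requested by the FDA for intranasal administration".

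Events outside the diary fall under Section 9.2, which records "AEs spontaneously reported by the subject or reported in response to an open question from the study personnel"; the same sentence goes on to include events found by observation. Section 12.7 defines the primary safety endpoint to cover both solicited and unsolicited events.

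**The concern.** The primary objective is to describe the safety profile, and reactogenicity is the first endpoint listed under it. For a nasal spray, the nasal symptoms are the core of that description. The protocol names runny nose as an expected local reaction in its background section and then does not ask about it after dosing.

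Three things follow:

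- Subjects are not prompted daily for it. Mild symptoms are the ones most easily missed without a prompt, and the earlier reactions were mostly mild.
- Related nasal symptoms are split. Congestion, sneezing and irritation go into the reactogenicity table on the diary scale. Runny nose goes into the adverse event table under a coded term.
- A summary of subjects with any local reactogenicity event leaves out those whose only local reaction is a runny nose.

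This is a gap in data collection, so no statistical analysis plan can repair it afterwards.

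**Working it through.** **1. Match the earlier trial's leading events to the solicited list.** The endpoint has 9 local events and 8 systemic events (7 symptoms plus fever), 17 in all.

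| Event in Section 2.6 | Solicited here? |
|---|---|
| Headache | Yes (systemic) |
| Sore throat | Yes (local) |
| Nasal congestion | Yes (local) |
| Nasal irritation | Yes (local) |
| Runny nose | No |

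Four of the five are solicited.

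**2. Does the congestion item cover it?** Section 2.6 lists the two symptoms separately, and exclusion criterion 16 joins congestion and rhinorrhea with an \"or\" as two presentations. The diary's anchors for congestion speak only of interference with activity and use of medication. Nothing tells a subject to enter a runny nose there.

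**3. Follow one subject.** Suppose a vaccinee has a runny nose for some days after dosing and no other local symptom.

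- Reactogenicity summary (Section 12.7.1): no row for the symptom, and the subject counts as having no local event.
- Adverse event summary (Section 12.7.1): counted by dose group if volunteered, elicited, observed or found on examination by Day 29.
- Grading: Section 9.4.1 instead of the diary guide. Grade 1 means no interference with activity on both. At Grade 3 the diary's congestion row needs only that daily activity is prevented, while Section 9.4.1 also requires medical intervention.

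**4. The plan's own figure.** Section 12.9 states an 80% probability of seeing at least one event with a true rate of 3.6% among 45 recipients: 1 − (1 − 0.036)^45 = 0.808. It reproduces, and the point does not depend on it.

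**5. Illustration of size.** The documents give no runny-nose rate, so both inputs here are assumptions. Table 1 gives 15 vaccinees per dose group.

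- True 14-day rate of 10% to 40%: 15 × 0.10 = 1.5 to 15 × 0.40 = 6 per dose group.
- Rate of 25%: 15 × 0.25 = 3.75. If unprompted routes catch 30% to 70% of what a diary row would catch, the adverse event table shows 3.75 × 0.30 = 1.1 to 3.75 × 0.70 = 2.6 of 15.

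**6. What a mid-study change would do.** Suppose the true rate is 25% in every cohort, the first cohort used the present diary and later cohorts have the added row. The reactogenicity table would then have no runny-nose entry for the lowest dose and an expected 3.75 of 15 at each higher dose, with no true dose effect. The summary of any local event would shift the same way, by the unknown share of subjects whose only local reaction is a runny nose.

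**The case against.** The strongest reply is that the list came from the regulator (Section 4.2.3), is the same wherever it appears, and contradicts nothing. That stands as far as it goes. But the sentence explains where the list came from; it does not say that the list is exhaustive or why this symptom was left out, and adding an item removes nothing that was requested.

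A reader might infer that a runny nose can surface only through an open question. The documents do not support that. Section 9.2 also takes spontaneous reports and observation. Section 7.7 requires an otorhinoscopic and nasopharyngeal examination on a structured form, scheduled 2 hours after dosing and on Days 4, 8, 15 and 29. The diary also tells subjects to be ready to discuss other health issues. These routes are real, but none is a daily graded self-report.

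A reader might also infer that the event is lost to the primary endpoint. It is not: Sections 12.7 and 12.7.1 count unsolicited events by dose group with 95% confidence intervals.

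Nor is a planned comparison with the earlier trial lost. The only external comparison in the protocol is of immunogenicity, against banked samples from a licensed vaccine.

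Finally, the earlier reactions were mostly mild, and Section 2.6 reports no significant difference from placebo in reactogenicity. The smaller 2002 trial does not list runny nose among its intranasal local events. This lowers the urgency. It does not set runny nose apart from sore throat, congestion and irritation, which come from the same sentence and are solicited. The highest dose here is also about 30 times the highest in the 2007 trial (1×10^11 / 3.3×10^9 = 30.3), so the earlier rates need not carry over.

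**Conclusion.** The point holds as a gap in solicitation. One of the five most common events in the earlier intranasal trial has no diary row, no prompt and no diary grade, and it does not count towards a local reactogenicity event. It remains countable as an adverse event within the primary safety endpoint, so the loss is in completeness of capture and in comparability with the other nasal symptoms, not in the event itself.

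Its size cannot be fixed from the documents. The figures of 1.5 to 6 of 15 per dose group, and 1.1 to 2.6 of 15 captured at a 25% rate, rest on assumed rates and capture fractions and are illustration only. The grading difference shown above is at Grade 3 and will matter little if reactions are mostly mild.

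That the 2007 study belongs to the same product line is read from the heading of Section 2.6 and from the reference in Section 2.5 to "clinical trials of earlier formulations of NasoVAX"; its sponsor is not named. The point does not depend on this. The change is worth making because it is cheap and bears on the first endpoint listed under the primary objective.

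**What to change.** Add runny nose to the local events in Sections 1.1, 3 and 7.3, and as a row in the Appendix 2 diary and its severity guide, with the same 0 to 4 anchors as nasal congestion.

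The documents do not say which cohorts have been dosed, but a version before the present one was already in use. If any cohort has used the present diary:

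- report runny nose by method of capture (diary or adverse event record), and show cohorts without the row as not solicited, not as zero;
- base the across-dose summary of any local event on the nine items now listed, so that differing solicitation does not create an apparent dose trend. A ten-item version can be shown for cohorts that had the row.

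The cost is one diary row, its severity anchors and text edits in three sections, made by amendment. The downsides are a somewhat higher reported local-event rate wherever the tenth item is counted, and no solicited runny-nose data for subjects already dosed.

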# **3 STUDY OBJECTIVES AND ENDPOINTS**

OBJECTIVES	ENDPOINTS			
Primary Objective				
• To describe the safety profile of NasoVAX in healthy adults when administered by intranasal spray at a single dose of 1×10  , 1×10  , or 1×10  vp	
 
Reactogenicity: counts and percentages of subject with local events (nasal irritation, sneezing, nasal congestion, cough, sore throat, change in smell, change in taste, change in vision, eye pain) and systemic events (headache, fatigue, muscle ache, nausea, vomiting, diarrhea, chills, fever) for 14 days after vaccination
 
AEs: counts and percentages of subjects with AE from Day 1 to Day 29; MAEs, SAEs, NCIs from Day 1 to Day 181
 
			
Secondary Objective				
• To evaluate the humoral immune response to NasoVAX when administered by intranasal spray at a single dose of 1×10  , 1×10  , or 1×10  vp	
 
Antibody level measured by HAI in serum:         
 
GMT: the antilog of the mean of the log-transformed titers
 
GMR: the ratio of postvaccination and prevaccination GMTs within the same dose group
 
SPR: the percentage of subjects with a HAI titer ≥ 1:40
 
SCR: the percentage of subjects with either a baseline HAI titer < 1:10 and a postvaccination titer ≥ 1:40 (which is 4 times the assay lower limit of quantitation), or a baseline HAI titer ≥ 1:10 and a 4-fold increase in postvaccination HAI titer relative to baseline
 
 
 
Antibody level measured by microneutralization in serum:         
 
GMT
 
Responder rate: the proportion of subjects with 2-fold and 4-fold rise since baseline
 
 
 
			

OBJECTIVES	ENDPOINTS			
Exploratory Objectives				
• To evaluate the cellular immune response to NasoVAX when administered by intranasal spray at a single dose of 1×10  , 1×10  , or 1×10  vp	
 
SFUs to HA peptides measured by enzyme-linke ELISpot in PBMCs:
 
Geometric mean SFUs
 
Responder rate
 
			
• To evaluate the mucosal immune response NasoVAX when administered by intranasal spray at a single dose of 1×10  , 1×10  , or 1×10  vp	
 
IgA antibody level measured by ELISA:
 
GMT
 
GMR
 
			

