#### 9.1.2 Medically Attended Adverse Event

An MAE is an AE resulting in hospitalization, emergency room visit, or visit to or from medical personnel (other than routine health care visits).

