#### 9.1.4 Serious Adverse Event

An AE or suspected adverse reaction is considered serious (an SAE) if, in the view of either the Investigator or Sponsor, it results in any of the following outcomes:

- Death
- Life-threatening (An AE is considered life-threatening if, in the view of either the Investigator or Sponsor, its occurrence places the patient or subject at immediate risk of death. It does not include an AE that, had it occurred in a more severe form, might have caused death.)
- Inpatient hospitalization or prolongation of existing hospitalization
- A persistent or significant incapacity or substantial disruption of the ability to conduct normal life functions
- A congenital anomaly/birth defect

Life-threatening means that the subject was at immediate risk of death at the time of the SAE; it does not refer to a serious AE that hypothetically might have caused death if it were more severe. Hospitalization does not include same day surgery, elective surgery, optional admission not

05 October 2017 Confidential Page 39 of 66

associated with a precipitating AE (ie, elective cosmetic surgery), or hospitalization planned before the start of the study for a pre-existing condition that has not worsened. Persistent or significant disability or incapacity means that there is a substantial disruption of a person's ability to carry out normal life functions.

Important medical events that may not result in death, be life-threatening, or require hospitalization may be considered serious when, based upon appropriate medical judgment, they may jeopardize the patient or subject and may require medical or surgical intervention to prevent one of the outcomes listed in this definition. Examples of such medical events include allergic bronchospasm requiring intensive treatment in an emergency room or at home, blood dyscrasias or convulsions that do not result in inpatient hospitalization, or the development of drug dependency or drug abuse.

If it is not certain that an event meets the above definitions of an SAE, contact the Medical Monitor to discuss.

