## 9.3 Recording of Adverse Events

An AE should be recorded individually in the study subject's own words (verbatim) unless, in the opinion of the Investigator, clarification of the subject's verbatim language is necessary or the AEs constitute components of a recognized condition, disease, or syndrome. In the latter case, the condition, disease or syndrome should be named rather than each individual symptom. The AE term will subsequently be coded using MedDRA.

The AE term, date of AE onset, date of AE resolution (if applicable), severity, causality, action taken for the AE, outcome and whether or not the AE is an MAE, NCI, and or SAE will be recorded.

05 October 2017 Confidential Page 40 of 66

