#### **Adverse Events**

The number (percentage, 95% CI) of subjects with AEs from Day 1 to Day 29 (including MAEs, NCIs, SAEs) will be summarized for each MedDRA system organ class and preferred term and by dose group and overall. The number (percentage) of subjects with MAEs, with NCIs, and with SAEs from Day 1 to Day 181 will be summarized in a similar fashion. The number (percentage, 95% CI) of subjects with AEs by severity and by relationship to IP will also be summarized.

Listings of AEs, MAEs, NCIs, and SAEs will be provided.

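### A non-serious diary reaction that leads to an office or ER visit gets no AE record under Sections 7.3 and 9.5, so the primary Day 1 to Day 181 MAE summary can be undercounted

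*Protocol*

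**What the plan says.** Section 7.3 sets the rule for solicited reactions: "A reactogenicity event recorded on the diary will not be recorded as an AE unless it meets the criteria of an SAE". Section 9.5 repeats it word for word. The only exception is seriousness. For reactions that outlast the 14-day diary, 7.3 adds: "If there are any events ongoing after the diary reporting period, these events will be followed until resolution and the stop date recorded". It does not say that they then become AEs.

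Section 9.1.2 builds the MAE on the AE: "An MAE is an AE resulting in hospitalization, emergency room visit, or visit to or from medical personnel", with routine health care visits excepted. Section 9.3 lists the fields of an AE record, among them "whether or not the AE is an MAE, NCI, and or SAE will be recorded".

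MAEs belong to the primary endpoint. Section 3 lists "MAEs, SAEs, NCIs from Day 1 to Day 181", and Section 12.7.1 summarizes the number and percentage of "subjects with MAEs, with NCIs, and with SAEs from Day 1 to Day 181".

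Section 9.2 carries the general instruction that all AEs, MAEs included, are recorded from consent to Day 29, and that MAEs, NCIs and SAEs are recorded after that. It does not mention the diary rule.

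**The concern.** Safety is the primary objective, and the MAE count is one of its named measures. The diary rule covers reactions first entered in the 14 days after dosing, which is the protocol's own window for vaccine reactions. If the rule is followed literally, the MAE summary omits medically attended solicited reactions unless they are serious. Anyone reading a table labelled Day 1 to Day 181 would take it as complete from Day 1.

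The protocol itself foresees such events: for every diary symptom, Grade 4 in Appendix 2 means an ER visit or hospitalization. An ER visit without admission is not a listed SAE outcome in 9.1.4.

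**Working it through.** **Step 1: follow an event through the definitions.** The route into the MAE summary is diary entry, AE record (7.3, 9.5), MAE flag (9.3), Day 1 to Day 181 summary (12.7.1).

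| Diary event | AE record under 7.3/9.5 | MAE flag | Where it shows |
|---|---|---|---|
| Sore throat, office visit, no diagnosis | No | No | Reactogenicity table at the symptom's grade; visit not shown |
| Headache, ER visit, sent home | No | No | Reactogenicity Grade 4, pooled with hospitalization |
| Fever of 40 °C or less, ER visit, sent home | No | No | Reactogenicity, at most Grade 3: subjects do not grade temperature (7.3) and Appendix 1 grades fever by degrees |
| Any symptom, admitted | Yes (SAE) | Yes | Both tables |

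Three routes can still open an AE record for the first three rows:

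- Section 9.1.4 says important medical events "may be considered serious when, based upon appropriate medical judgment, they may jeopardize the patient or subject". This is a judgment.
- Section 9.3 says that, where AEs form part of a recognized condition, "the condition, disease or syndrome should be named rather than each individual symptom". This needs a diagnosis.
- Section 9.5 records clinically significant laboratory, examination, ECG or vital sign findings. This needs a finding, for example a temperature that the investigator judges significant.

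None of these covers a plain visit for a listed symptom. No diary grade is defined by a doctor visit. Outpatient IV hydration (vomiting, diarrhea) and narcotic medicine (a few symptoms) come closest. The general AE scale in 9.4.1, by contrast, does name a doctor visit, under Grade 3.

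**Step 2: the plan's own figures.** Section 12.9 gives 80% for at least one AE among 45 at a rate of 3.6%: 1 − (1 − 0.036)^45 = 0.808. It gives a 5% one-sided 90% upper bound for 0 of 45: 1 − 0.1^(1/45) = 4.99%. Both reproduce. Neither measures missed MAEs; they are background.

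**Step 3: size per missed subject.** Group sizes are from Table 1; intervals are exact (Clopper-Pearson) 95%, shown for scale.

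- Dose group: 1/15 = 6.7% (0.2 to 31.9%) becomes 0/15 = 0% (0 to 21.8%), a loss of 6.7 points.
- All NasoVAX: 1/45 = 2.2% (0.1 to 11.8%) becomes 0/45 = 0% (0 to 7.9%), a loss of 2.2 points.

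The summary counts subjects, so the percentage falls only if the subject has no other recorded MAE.

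**Step 4: how often.** The protocol gives no rate for non-serious, medically attended diary reactions. The rates p below are assumptions; 3.6% is borrowed from 12.9 only as a convenient point. P(at least one) = 1 − (1 − p)^n.

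| Assumed p | n = 15 | n = 45 | Expected in 45 |
|---|---|---|---|
| 1% | 14% | 36% | 0.45 |
| 2% | 26% | 60% | 0.9 |
| 3.6% | 42% | 81% | 1.6 |
| 5% | 54% | 90% | 2.3 |

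These are chances that such a reaction occurs, not that it goes uncounted; the three routes would recover some.

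**The case against.** The best counter-argument is Section 9.2, which orders all AEs including MAEs to be recorded to Day 29. Section 12.7 also speaks of solicited and unsolicited AEs, and the AE definition in 9.1.1 is broad enough to include a diary reaction. On that reading, 7.3 only says which form a reaction goes on, and a medically attended one is still an MAE. This stands in part: the text contains two instructions that conflict, so the undercount is possible rather than certain. The diary rule is nevertheless the more specific instruction, it is stated twice, and the MAE flag exists only on the AE record.

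The visit may also reach site records. Subjects are asked about interim medical history at each visit (4.1), the investigator reviews the diary (7.3), and the study nurse collects details when medication or treatment is ticked (Appendix 2). That stands too, but the protocol does not carry this information into the MAE count. An analysis plan could recover it only if it were captured in usable form.

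A reader might go further and infer that safety information is lost. The documents do not support that. The reaction stays in the reactogenicity tables by severity, themselves part of the primary endpoint, and the Safety Review Committee reviews reactogenicity before each escalation (6.5). Keeping solicited reactions apart from AE records is a legitimate way to avoid double reporting.

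**Conclusion.** The point holds as a conflict of wording with a modest consequence. Under the specific diary rule, the primary MAE summary can miss non-serious solicited reactions that led to an office or ER visit, including a visit after Day 14 for a reaction already on the diary. What can be lost is the MAE count and the visibility of the visit. Each missed subject with no other MAE costs 6.7 points in a dose group or 2.2 points over all NasoVAX recipients.

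The frequency is unknown and probably low. Section 2.6 reports mostly mild events in the two earlier trials, though at doses similar to or below the lowest dose here. No stated decision rule uses the MAE count, and the analyses are descriptive.

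A reader might also infer that severe diary reactions fall outside the stopping criteria in 6.6, because those count AEs. The text does not establish that: 9.1.1 and 12.7 suggest that solicited events do count. It forms no part of this point. This is a minor, inexpensive improvement.

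**What to change.** In 7.3 and 9.5, widen the exception so that a diary reaction is also recorded as an AE when it is medically attended as defined in 9.1.2, alongside the existing SAE exception. Keep the event in the reactogenicity tables, and footnote the AE and MAE tables to mark events that appear in both. Give the site a matching eCRF instruction. The change also removes the conflict with 9.2 for these events.

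The cost is one phrase in two sections, a few more AE records and some double listing. No extra visits, samples or subjects are needed.
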